## A. Implementation study

This section describes the research questions, the data used to answer the research questions, and the methods used to analyze the data and describe the findings of the process or implementation study.

### 1. Research questions

The research questions for this implementation study relate to fidelity to, and engagement with, the planned multistep CQI process. The implementation study seeks to understand how closely the CQI process followed the original outlined plan and how understandable, useful, and engaging program staff found each step of the CQI process. Additionally, the implementation study seeks to understand what contextual factors affected the implementation of the multistep CQI process and to identify best practices and lessons learned about implementing a CQI process that could be shared with the broader field.

**Table 5.** Research questions for each implementation element

Implementation element	Research question
Fidelity	
 
To what extent were the five steps of the CQI process carried out as intended each grant year?
 
What were the unplanned adaptations to the key CQI process components?
 

Implementation element	Research question
Engagement	
 
• How understandable did CQI team members, and program staff broadly for Step 2 and Step 4, find the reports for each step of the CQI process?
 
• How engaged were CQI team members and program staff in each step of the CQI process?
 

Context	
 
• How well did the implementation of the multistep CQI process go for program and evaluation staff?
 
• What external events affected the implementation of the multistep CQI process?
 
• What are some best practices and lessons learned for improving the multistep CQI process?
 

## 2. Implementation evaluation enrollment

The implementation study was initially approved along with the outcome study by Solutions IRB on 03/29/2021 and has been annually reviewed and approved three times on 03/15/2022, 03/07/2023, and 3/11/2024. Additionally, revisions to the study were submitted as amendments and were approved on 05/17/2022, 02/15/2023, and 08/29/2023.

The sample for the implementation evaluation is made up of staff from Anthem Strong Families. The final report will include information about staff demographics, role types, and participation levels. Permanent members of the CQI team are surveyed after each step of the CQI process has been completed, and the program staff more broadly are surveyed after reviewing Step 2, 3, and 4 reports that are relevant to the service sites where they work with participants. Staff are also interviewed during annual site visits.

Because the data sources for the implementation evaluation are staff satisfaction surveys that are not administered to program participants, no consent is collected, and no incentives are offered for survey completion.

## 3. Data sources and data collection

The data sources for the implementation evaluation are CQI process tracking logs (See Appendix C), staff satisfaction surveys administered on Qualtrics (see Appendix A), and staff interviews.

The evaluation lead and data manager from Midwest Evaluation and Research are responsible for tracking and logging the delivery of interventions and reports that are associated with each step of the multistep CQI process. When program staff decide on a targeted intervention to implement at a given site, evaluators document when (with which cohort, or on which specific date) and where (which service site or sites) the intervention is being put into place. The date that each CQI report is delivered is also documented. Additionally, CQI meeting attendance is tracked on an ongoing basis after each bi-weekly meeting to assess CQI team engagement with the process.

The evaluation lead is responsible for creating and administering staff satisfaction surveys for each step of the multistep CQI process. After reviewing Step 2, 3, and 4 reports annually with the CQI team, anonymous satisfaction surveys are delivered to CQI team members by the evaluation lead using an anonymous Qualtrics link via email. Although Step 1 reports are delivered bi-weekly to CQI team members, satisfaction surveys for the Step 1 reports are sent out annually. After the Program Director presents Step 2 and Step 4 annual reports with relevant program staff during staff meetings, an anonymous satisfaction survey is sent

to staff members using an anonymous Qualtrics link via email. Satisfaction survey instruments can be found in Appendix A.

Additionally, staff interviews during annual site visits provide more information about lessons learned, best practices, how CQI findings are being applied to program implementation, and suggestions for improving the CQI multistep process. MER evaluation staff will also reflect at the end of the project on successes and challenges related to the implementation of the multistep CQI process to inform future CQI efforts.

**Table 6.** Data for addressing the implementation research questions

Implementation element	Research question	Data source	Timing and frequency of data collection	Party responsible for data collection
Fidelity	To what extent were the five steps of the CQI process carried out as intended each grant year?	CQI process tracking log (See Appendix C)	Updated after each step of a CQI cycle	Evaluation lead and/or data manager
Fidelity	What were the unplanned adaptations to key CQI process components?	CQI process tracking log (See Appendix C)	Ad hoc	Evaluation lead and/or data manager
Engagement	How understandable did CQI team members, and program staff broadly for Step 2 and Step 4, find the reports for each step of the CQI process?	CQI team satisfaction surveys; staff satisfaction surveys (See Appendix A)	Annually after the completion of each step of the CQI process has been completed	Evaluation lead
Engagement	How engaged were CQI team members and program staff in each step of the CQI process?	CQI team satisfaction surveys; staff satisfaction surveys (See Appendix A)	Annually after the completion of each step of the CQI process has been completed	Evaluation lead and/or data manager
Engagement	How engaged were CQI team members in meetings?	CQI team meeting attendance logs (See Appendix B)	Bi-weekly after each CQI team meeting	Evaluation lead
Context	• How well did the implementation of the multistep CQI process go for program and evaluation staff?	Staff interviews; evaluator retrospective	Annually during site visits	Evaluation staff
Context	What external events affected the implementation of the multistep CQI process?	Staff interviews; evaluator retrospective	Annually during site visits	Evaluation staff

---

Implementation element	Research question	Data source	Timing and frequency of data collection	Party responsible for data collection
Context	What are some best practices and lessons learned for improving the multistep CQI process?	Staff interviews; evaluator retrospective	Annually during site visits	Evaluation staff

**Family Champions Project
Statistical Analysis Plan**

Clinicaltrials.gov ID: NCT05298345

September 4, 2024

Analysis approach

To assess the association between the multistep CQI process and the outcome measures, trends in dosage, retention, and survey response rates will be assessed over time since the start of the program. If the CQI process has been effective in identifying and addressing issues that require intervention, we would expect that program implementation would get stronger over time, as measured by progress toward meeting programmatic targets for these measures.

Analytic sample

The analytic sample for RQ1 and RQ2 is made up of the participants who received services at the facilities that received CQI intervention efforts as part of the multistep CQI process. The aggregated dosage, retention, and survey response rate data for these participants will make up the analytic sample.

The analytic sample for the secondary research questions (RQ3 and RQ4) about participant healthy partner relationship attitudes will be defined as participants who have complete baseline and outcome data for the constructed outcome measure (complete case). Because these relationship questions are only shown to participants who report currently being in a romantic relationship, participants can only have complete case survey data if they report being in a relationship at both waves of data collection. As mentioned above, participants will only be included in the analytic sample if they have one or no missing values for the five items used to construct this outcome measure (80% or 100% of non-missing items). Participants who do not meet this threshold will have their outcome value assigned to missing and will not be included in the analytic sample; no imputation is planned for the outcome data.

Data preparation

Program-level and participant-level data will be downloaded as an Excel file using nFORM's data export feature. The data sets will be cleaned and prepared for analysis using the R Studio statistical software package. All files will be exported into R and cleaned separately before data sets are merged into a final, wide format file for analyses using nFORM client ID as the unique identifier for matching programmatic (dosage, client status, survey response rates) and participant survey data.

Analytic approach

The analysis for this evaluation will be completed using Excel and the R Studio statistical software package. Trends in programmatic outcome measures will be assessed descriptively over time using graphs that show average dosage, attrition, and survey response rates by month since program start among participants who enrolled in that month. Trends in program-level (cross-site) averages will be assessed for improvements over time, and trends in site-level averages will be assessed both for improvements since program start and immediately following the implementation of targeted interventions, which will be noted on the graphs. Site-level averages will be compared across the full study time period. Assuming the continuous, rapid cycle learning and intervention of the multistep CQI process is happening as planned, average metrics are expected to improve over time and immediately following interventions.

For the secondary research question 3 analysis, a change score will be calculated for each complete case respondent using their average at program entry and their average at program exit. We will use paired sample

t-tests to assess the magnitude and significance of mean score changes among program participants in the analytic sample. For the secondary research question 4 analysis, a basic regression model will be used to determine if higher dosage of primary workshop hours is associated with higher average scores on attitudinal items. Findings are considered statistically significant based on a $p < 0.05$, two-tailed test.

Attrition

Sample attrition is not a concern for the programmatic measures assessed for RQ1 and RQ2.

For the secondary research questions, sample attrition is related to program retention, as participants can only have complete case data if they stay in the program to take their nFORM exit survey. Anthem Strong Families staff have implemented numerous strategies to increase participant retention. Retention is tracked on an ongoing basis as part of the bi-weekly CQI team meetings between Anthem and MER staff, so decreases in survey response rates or participant retention can be tracked and addressed in real time as cohorts are enrolled in the program.

Sample attrition at the participant outcome level will be reported descriptively in the final report. We plan to report the proportion of total program enrollees that is missing for the outcome measure and for what reason (e.g., survey non-response, not eligible to answer relationship questions, exceeded 20% threshold for item missingness within the construct).

Implementation Analysis

Analysis approach

To address these implementation research questions, we will analyze a combination of quantitative and qualitative data. Some quantitative measures of fidelity and engagement will be counts with no calculations required (e.g., number of reports, number of meetings attended, etc.). Engagement measures that use staff survey data will involve simple percentage calculations of the number of responses that rated understandability and feeling welcome as Somewhat Agree or higher, reported descriptively. The sample size of the engagement measures will be the number of survey responses received from the CQI team and broader program staff. Survey responses will be checked for completeness, and we will also ensure that answer levels are numerically coded, and reverse-code where necessary. For the qualitative measures related to context, the evaluation team will summarize broad themes that arise during staff interviews about lessons learned, barriers to implementing CQI, and best practices for the field. The sample size for the context measures will be the number of interviews conducted during site visits. Interview data will be analyzed for key themes by the evaluation lead.

Measures for addressing the implementation research questions

Implementation element	Research question	Measures
Fidelity	To what extent were the five steps of the CQI process carried out as intended each grant year?	
 Total number of reports delivered for each step of the CQI process Timing of report delivery for each report delivered Number of targeted interventions implemented at each service site
Fidelity	What were the unplanned adaptations to key CQI process components?	
 List of unplanned adaptations, such as in report timing or CQI process components cut
Engagement	How understandable did CQI team members, and program staff broadly for Step 2 and Step 4, find the reports for each step of the CQI process?	
 Percent of responses in which CQI team members and/or program staff score “Somewhat agree” or higher that they understand the information presented in each report (survey questions are tailored to how much of the CQI process a team member is seeing, with frontline staff being surveyed after Step 2 and Step 4 reports, and CQI team members being surveyed about all steps).
Engagement	How engaged were CQI team members and program staff in each step of the CQI process?	
 Percent of responses in which CQI team members and/or program staff score “Somewhat agree” or higher that their input was welcome in the discussion of each report Attendance at CQI team meetings by key CQI team members
Context	How well did the multistep CQI process work?	
 Qualitative assessments of how well the multistep CQI process was implemented (compared to the original plan) and how well it worked for program staff at all levels
Context	What external events affected the implementation of the multistep CQI process?	
 Description of challenges or barriers to implementing the multistep CQI process overall and to implementing improvement strategies at specific sites
Context	What are some best practices and lessons learned for improving the multistep CQI process?	
 Description of what lessons learned or best practices were most effective for implementing a CQI process

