#### 1. **Step 1: Real-Time Performance Assessment Reports (prepared and presented bi-weekly by evaluation lead and/or data manager)**

- a. Report description - use key indicators to track overall performance trends.
- b. Purpose –
  - i. Provide real time monitoring of data entry and progress toward key metrics
  - ii. Familiarize CQI team staff with metrics that will be monitored and discussed throughout the lifetime of the project and in subsequent reports (Steps 2-5)
- c. Fidelity tracking – number of CQI team meetings scheduled and held where Step 1 CQI reports are presented to the CQI team
- d. Dosage tracking -
  - i. Intended vs. actual amount received – attendance of all CQI Team members at meetings for Step 1 Reports (i.e., number, names, roles) documented on CQI Team Tracking Sheet
- e. Performance Intervention Tracking – CQI Tracking Sheet for Performance Issues and Interventions (ongoing entry and revision as needed)
- f. Feasibility Assessment –
  - i. Focus on utility and user-friendliness of Step 1 report
  - ii. CQI Team Survey for Step 1: administered each program year to permanent staff on the CQI Team

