- a. Report description – examine performance trends before and after an intervention at each site, looking for improvements and comparing to the relevant standards
- b. Purpose – assess results of interventions on performance outputs to determine whether improvements were made for the relevant standard
- c. Fidelity tracking –
  - i. Intended amount to be offered based on intended report timeline
  - ii. Actual amount offered (# CQI Team meetings scheduled on Outlook, # CQI Team meetings where Step 4 CQI Report presented to CQI Team, # Step 4 reports created)
- d. Dosage tracking –
  - i. Intended amount received – attendance of all members at CQI Team meetings for Step 4 Reports (i.e., number, names, roles)

- ii. Actual amount received – CQI Tracking Sheet for Team Attendance for Step 4 Reports
- e. Feasibility assessment –
  - i. Focus on utility and user-friendliness of Step 4 report
  - ii. CQI Team Survey for Step 4: administered each program year to staff on the CQI Team
  - iii. FCP Staff Survey for Step 4: administered each program year to all frontline staff who develop performance interventions with the CQI team

**Table 1.** Description of intended intervention components, content, dosage and implementation schedule, delivery, and focal populations

Components	Content	Dosage and schedule	Delivery	Focal population
CQI Process Step 1	Monitoring overall and recent program performance using nFORM operational reports, local evaluation survey data, and the query tool	Reports are prepared bi-weekly and discussed at bi-weekly, hour-long CQI team meetings	Virtual CQI team meetings are held bi-weekly on Tuesday mornings; the evaluation lead facilitates meetings, and Step 1 reports are presented by the evaluation lead and/or data manager	CQI team members (program director, program manager, evaluation lead, data manager(s))

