CQI Process Step 2	Monitoring the same performance metrics as presented in the Step 1 report, but broken down by service site using nFORM operational reports, local evaluation survey data, and the query tool	Reports are prepared annually in the second quarter of each grant year and discussed at standing CQI team meetings and program staff meetings	Existing CQI team meetings are used to present and discuss Step 2 report findings; the evaluation lead facilitates the meetings and presents the Step 2 reports to the CQI team. Following the CQI team discussion, program leadership shares the Step 2 report findings with front line staff during staff meetings to solicit ideas for interventions	CQI team members (program director, program manager, evaluation lead, data manager(s); rotating front line staff member); Anthem program staff (case managers, facilitators, recruitment and retention specialists) who work at the sites being discussed in the Step 2 reports
CQI Process Step 3	Offering the same conclusions as the Step 2 report but focusing on one service site per Step 3 report; uses nFORM operational reports, local evaluation survey data, and the query tool	Reports are prepared annually in the second quarter of each grant year and discussed at standing CQI team meetings	Step 3 reports are sent to the program director who distributes each site's Step 3 report to the relevant program staff who work at that site	CQI team members (program director, program manager, evaluation lead, data manager(s)); program staff for specific sites (case managers, facilitators)

Components	Content	Dosage and schedule	Delivery	Focal population

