	prior to undergoing observation of their group facilitation. Once completed, they are considered a certified TYRO curriculum facilitator.	facilitation or case management training is offered through targeted webinars or staff development sessions.
CQI process	At the beginning of the grant cycle, Anthem held a 3-day training to discuss the specifics of the grant and evaluation, and the purpose and process of CQI were discussed in detail at this initial training. As new staff are onboarded, they receive an explanation of the purpose and process of CQI, both from program leadership and from more experienced staff.	The purpose and process of CQI is reinforced on an ongoing basis. Starting with more experienced staff who fully understand their day-to-day roles, frontline staff are invited to sit in on CQI team meetings on a quarterly rotating basis to help them understand the value of the CQI process and how their role fits into the larger picture. CQI report findings are discussed with staff at weekly staff meetings.

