### 1. Research questions

RQ1.1: Did the multistep CQI process support changes in primary workshop dosage, program attrition rates, or survey response rates at the program level?

RQ2: Did meaningful improvements in primary workshop dosage, survey response rates, or program attrition rates vary by service site *for sites that focused on improving the same metrics?*

RQ3 [secondary]: Do participants report healthier partner relationship attitude outcomes after program participation, as compared to baseline?

RQ4 [secondary]: Was level of dosage associated with reporting healthier partner relationship attitude outcomes after program participation, as compared to baseline?

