### 2. Outcomes evaluation enrollment

This study was initially approved by Solutions IRB on 03/29/2021 and has been annually reviewed and approved on 03/15/2022, 03/07/2023, and 3/11/2024. Additionally, revisions to the study were submitted as amendments and were approved on 05/17/2022, 02/15/2023, and 08/29/2023.

Participants for the program, and thus the study, are recruited primarily from community partnerships, walk-ins to Anthem Strong Families, radio and social media advertising, and word of mouth referrals.

Program service locations have varied throughout the implementation of the program but have included:

---

- Schools
  - Stephen C. Foster Elementary School
  - Herbert Marcus Elementary School
  - Burnet Elementary School
- Treatment Centers / Transitional Facilities
  - Soul's Harbor Treatment Center
  - Free Man House Transitional Living Facility
  - Shurrun's House Sober Living Facility
  - Gateway Foundation Treatment Center
- Vickery Meadow Youth Development Foundation
- Buckner Children and Family Services, Family Hope Center at Bachman Lake
- Virtual services provided via Zoom

The projected enrollment and desired sample size for the study is 800 participants. The final report will include a breakdown of the number of sites, number of staff at each site, and number of participants at each site.

To be eligible for the program, and thus the study, participants must be 1) low-income individuals, 2) at least 18 years of age, 3) with no open criminal cases (can be deferred), and 4) able to speak and understand English or Spanish.

Consent for enrollment into the evaluation happens during program orientation, prior to the start of the first primary workshop. A consent form is provided to participants, and a script is read by either the facilitator or the data manager, explaining the study activities and the potential risks and benefits. Participants sign and date the consent form and return it to the data manager, who logs the record in a consent spreadsheet on MER's secure Dropbox.

Enrollment into the study began April 22, 2021 and is estimated to conclude February 15, 2025.

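### The RQ1 program-level trend cannot separate CQI from maturation, site mix or outside conditions, so the SAP should not read improvement alone as a sign that CQI worked

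*SAP*

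**What the plan says.** Protocol section B.1 puts RQ1.1 as a question about the contribution of CQI: "Did the multistep CQI process support changes in primary workshop dosage, program attrition rates, or survey response rates at the program level".

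The SAP (Analysis approach) answers it with time trends: "trends in dosage, retention, and survey response rates will be assessed over time since the start of the program". It then states what an effective CQI process should look like: "we would expect that program implementation would get stronger over time, as measured by progress toward meeting programmatic targets for these measures". Under Analytic approach, program-level averages are graphed by enrollment month and inspected for improvement. Only site-level averages are also examined just after targeted interventions. Under Analytic sample, RQ1 and RQ2 use participants at facilities that received CQI intervention efforts.

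Three parts of the protocol bear on when CQI began:

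- Table 2, on CQI training, where the purpose and process of CQI were covered: "At the beginning of the grant cycle, Anthem held a 3-day training to discuss the specifics of the grant and evaluation".
- Table 1, on Step 1: "Reports are prepared bi-weekly and discussed at bi-weekly, hour-long CQI team meetings". No later start date is given.
- Section A, Step 1, on its purpose: "Familiarize CQI team staff with metrics that will be monitored and discussed throughout the lifetime of the project".

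The site-specific steps come later. For Step 2, Table 1 says: "Reports are prepared annually in the second quarter of each grant year and discussed at standing CQI team meetings and program staff meetings". On the sites themselves, section B.2 says: "Program service locations have varied throughout the implementation of the program".

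**The concern.** A trend since program start can speak to CQI only if time under CQI differs from time since program start, or if some participants were served without CQI. The plan defines neither contrast at program level. Three other processes ran over the same calendar: staff became more experienced, the set of service sites changed, and outside conditions moved after April 2021. Each could improve the metrics without any help from CQI, and the SAP adjusts for none of them.

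The protocol describes the CQI cycle as the main intervention under test, so the first research question could be answered by a pattern that would arise equally well without it. A funder or another program reading the final report could then take background improvement as support for the CQI model.

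**Working it through.** The plan states no effect size, power or threshold for RQ1, so there is no figure to reproduce. The check is whether a CQI effect can be identified, followed by an illustration.

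**Inputs from the documents.** Enrollment runs from 22 April 2021 to 15 February 2025 (Protocol B.2): 1,395 days, and 1,395 / 30.4375 = 45.8 months, taken as 46. Projected enrollment is 800 (Protocol B.2).

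**Step 1: identifiability.** Write the monthly program-level mean as a + b·t + c·(CQI on) + d·(time since CQI start), with t = 0 to 45. If CQI is on from month 0, the indicator equals the intercept column and time since CQI equals t. The design matrix then has rank 2 of 4, and c and d cannot be separated from a and b. Allowing a lag before the first CQI-driven action (lags assumed):

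| Months before CQI takes hold | Rank of 4 |
|---|---|
| 0 | 2 |
| 1 | 3 |
| 3, 6 or 12 | 4 |

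A lag of three months or more would make the terms algebraically separable. The SAP defines no such segment and plans no such contrast at program level.

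**Step 2: illustration with zero CQI effect.** The 800 participants are spread evenly over 46 months (18 months of 18 and 28 months of 17: 324 + 476 = 800). Each has a yes/no outcome such as survey completion. The success rate starts at 60%, 70% or 80% and drifts up linearly by a fixed total over the study for reasons unrelated to CQI. A weighted least-squares slope is fitted to the monthly proportions, with 20,000 runs per setting. Baselines and drifts are assumptions; the documents give neither.

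| Total background drift | Runs with a favorable slope (range over baselines) |
|---|---|
| 0 points | 49% to 50% |
| 5 points | 81% to 86% |
| 10 points | 96% to 99% |
| 15 points | 99.6% to about 100% |

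For attrition, read the same table with a downward slope. With no drift, about half of the runs still lean the favorable way, because the plan sets no numeric size for improvement. Adding a significance test would not solve the problem. At a 10-point drift, a two-sided 5% test finds a significant improvement in 43% to 65% of runs. In those runs the improvement is real, but CQI did not cause it.

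**Step 3: is the gap filled elsewhere?** The dated interventions marked on graphs (SAP, Analytic approach), the site baseline data (Protocol B.4) and the Step 4 before-and-after reports (Protocol section A) all work at site level. They help RQ2 more than RQ1. External events are a research question in the implementation study, addressed by staff interviews and an evaluator retrospective. Those can inform interpretation but do not adjust the trend.

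**The case against.** The strongest defense is that the plan is openly descriptive. The SAP speaks of association and states an expectation in one direction: effective CQI implies improvement. A reader might infer that the SAP declares any rising metric to be proof that CQI worked, or that it would reach that answer whatever happened. The documents do not support this. The converse is never written, flat or worsening metrics would count against the expectation, and for attrition the favorable direction is down. Protocol B.4 also looks at whether targets were reached and whether improvements were meaningfully large, though it gives no number for the latter. What remains is that improvement is the only program-level criterion offered for RQ1.1, so answering that question requires the converse in practice. Reaching a target does not show what moved the metric either.

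A reader might also infer that CQI is documented as running from the first day. It is not. The training, the bi-weekly Step 1 schedule and the project-long monitoring make it a strong inference, but no first report is dated, and site-specific work follows in quarter 2 of a grant year. If CQI took hold some months in, an earlier segment would exist. The plan does not use one.

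Finally, Protocol B.4 promises a look at change after intervention strategies, having introduced both RQ1 and RQ2. The SAP carries this through only for site-level averages.

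**Conclusion.** The point holds for RQ1. The program-level trend describes change while CQI was in place and cannot by itself attribute that change to CQI. A favorable trend could be credited to CQI when CQI had no effect.

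The size of any misattribution cannot be derived from the documents. The simulation shows only that modest background improvement would usually look like the expected CQI result, and it rests on assumed baselines, an assumed linear drift and even enrollment. The identifiability argument rests on CQI having begun at about the start of the grant cycle and on the SAP's restriction to facilities that received CQI intervention efforts.

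The point does not extend to RQ2 in the same form, because dated site interventions give some before-and-after information there. Nor does it follow that a regression must replace the descriptive design. The data remain usable; what needs correcting is what RQ1 may conclude.

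**What to change.** **Required.** In the SAP (Analysis approach and Analytic approach), change how RQ1 is read. Report the program-level trend in each metric as change during the CQI period, and name the favorable direction for each, with a fall for attrition. State that improvement alone is not evidence that CQI produced it, since staff experience, site mix and outside conditions could produce the same trend. This takes a few sentences and no new data. The price is a more modest RQ1 claim.

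**Optional, as a supportive analysis of targeted interventions and not of CQI as a whole.** The evaluators already document when and where each targeted intervention starts (Protocol, Implementation study, section 3). For each metric, compare participants enrolled before and after a site's intervention with those at sites not yet targeted on that metric. Include site and calendar-time terms and site-clustered uncertainty, and report the estimate with a 95% confidence interval. Four limits should be stated with it:

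- Comparison sites still receive program-wide Step 1 CQI, so the result is closer to RQ2.
- Metrics at or near target are not selected for intervention (Protocol B.4), so regression to the mean will favor improvement afterwards.
- The comparison depends on sites being targeted at different times, and the restricted sample may leave few comparison sites.
- The data are thin. Protocol B.2 lists 10 locations, and enrollment touches 16 calendar quarters, so 800 / (10 × 16) = 5 participants per cell on average, at sites that changed over time.
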